Samples for microbiome analysis were collected at baseline (Visit 1), Day 14 (Visit 2), and Day 90 (Visit 4). Before collecting samples, each patient was asked to rinse with plain water prior and rest for 5 minutes. Sample collection was performed by gently wiping the buccal and tongue mucosa separately 10 times with three different cotton swabs. Samples were allowed to air dry at room temperature and individually placed in labeled containers with the patient's unique sequential subject identification number and day of collection. These samples were stored in a secure location at -20°C until utilized for microbiome analyses.

[4] Study Design Table

Protocol Study Design and Schedule of Assessments

Evaluation	Screening (0-2wks to Baseline)	Baseline (Visit 1) Day 0	Visit 2 Day 14 (± 3 d)	Visit 3 Day 45 (± 7 d)	Visit 4 Day 90 (± 7 d)
Informed Consent	x				
Inclusion / Exclusion	x	x			
Demographics	x				
Pregnancy Test		x			x
Medical History / Update	x	x	x		x
Medications / Update	x	x	x		x
Periodontal History	x		x		x
Oral Examination	x	x	x		x
Collect Specimen w Swab		x	x		x
Modified Gingival Index / MGI		x	x		x
Bleeding On Probing / BOP	x				x
Probing depth	x	x			x
Turesky modification Plaque Index		x	x		x
Scaling	x				
Eligibility	x				
X-rays		x			x
Enrollment / Randomization		x			
Dispense oral hygiene kit / Diary		x			
Schedule next appt	x	x	x		
Collect residual oral hygiene kit with Diary and distribute oral hygiene kit with Diary for next phase			x	x	
Collect residual oral hygiene kit / Diary					x

[5] Protocol Synopsis

1. Study Title: The Efficacy and Safety of stabilized chlorine dioxide mouth rinse in Therapy of Peri-implant mucositis
2. Study Design: Single Center, randomized, double blind masking, parallel, two-arm clinical study.
3. Objective: The purpose of this study was to analyze efficacy of stabilized chlorine dioxide as a chemical adjuvant for treatment of peri-implant mucositis in a non-surgical treatment protocol with a 3-month follow-up.
4. Study Treatments: 1) Stabilized chlorine dioxide (associated with periodontal basic therapy); and 2) control (placebo associated with periodontal basic therapy).
5. Number of Patients: A total of 54 patients in one clinical site at Stony Brook were randomized, 27 patients received 1) Stabilized chlorine dioxide (associated with periodontal basic therapy); and 27 patients received 2) control (placebo associated with periodontal basic therapy).

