6. Study Duration and Visits: The study duration was (3 months) and was comprised of a total of 4 visits: Screening and hygienic phase therapy (weeks -2 to -1), Baseline (Visit 1, Day 0), Visit 2 (14 days), Visit 3 (45 days), Visit 4 (90 days).
7. Subjects received an Oral Hygiene Kit at Visit 1. The Modified Gingival Index (MGI), Bleeding on Probing (BOP) and Plaque Index (PI), Pocket depth and radiographs were measured, and all oral tissues examined (baseline examination). Subjects returned for Visit 2 in 14 days \pm 3 days to: 1) assess and record changes in indices and oral health and any adverse conditions. Visit 3 (45 days \pm 7) was a compliance visit for study drug utilization. Visit 4 (90 days \pm 7) was a repeat of Visit 1. Samples for microbiome analysis were collected at baseline (Visit 1), Day 14 (Visit 2), and Day 90 (Visit 4).
8. All parameters for clinical exam were calibrated between the examiners involved with the study.

[6] Study Materials (Oral Hygiene Kit)

STUDY DRUG

Both the active and placebo drugs were provided in liquid form, intended for oral administration. Sample products were labeled by the manufacturer and shipped directly to the site.

ADMINISTRATION

After tooth brushing in the morning and evening, the study product was administered orally using a cup that measures 15 mL of oral rinse, swishing in the oral cavity for 30 seconds and expectorating.

[7] Subjects

Subject recruitment occurred at the discretion of the Principal Investigator. After being recruited, potential subjects were informed of the purpose of the study and guided through HIPAA documentation and the informed consent process. Upon their understanding of the study, HIPAA regulations, and their agreement with the terms of the informed consent, subjects indicated so by signing the forms. The eligibility of potential subjects was determined through a series of screening interviews and an oral examination. Following screening, those potential subjects who retained eligibility were enrolled in the study at the discretion of the Principal Investigator. Approximately 75 subjects were screened to provide 54 enrollees. Once these subjects were randomized, study enrollment was complete.

Number of subjects: 54 subjects

Age: 18 years to 80 years

Gender: Both male and female subjects entered this study.

Remaining Natural Teeth: Minimum of 20

[8] Subject Eligibility Criteria

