Once a subject had been screened and qualified for study participation, that subject was enrolled and assigned the next available randomization number. The study randomization table was generated by a third-party statistician. This procedure was used to keep the Study Statistician blinded to subject treatments prior to database lock.

WITHDRAWAL

Subjects enrolled in the study were able to elect to withdraw at any time for any reason. Additionally, subjects were able to have been withdrawn from the study at the request of the Principal Investigator for the following reasons:

1. An adverse event required discontinuation of the study rinse in the judgment of the Principal Investigator or designee
2. Subject refused or failed to comply with the study protocol

3. There was a protocol violation(s) or deviation(s) that compromised the use of the subject's data

All patients withdrawn from the study by request or by the Principal Investigator were to be seen, if they consented, for a close-out evaluation. The reason for withdrawal would be recorded by the Principal Investigator or designee on the End of Study form. Patients who experienced complications and discontinued the study on their own were to be scheduled, if they consented, for an immediate follow-up/close-out examination to determine whether an adverse event was present, and if so, the causation of the adverse event was to be recorded. If treatment was needed for any adverse event causing withdrawal, the subject would be monitored until there was a return to normal conditions. (Every effort would be made to follow up with subjects who withdrew from the study.)

Test Product: ClōSYS® Ultra Sensitive Rinse

Placebo: Oral rinse comprising same ingredients as in test product except for stabilized chlorine dioxide.

Materials:

Sponsor shipped prelabelled 'Oral Rinse A' and 'Oral Rinse X' products to the Test Site. Both products were in 16 oz. size bottle and identical in appearance.

Each subject received the following supplies at Baseline (Visit 1) i.e. supplies for 0-14 days:

- a. 1 bottle (16oz) of either Oral Rinse A or Oral Rinse X))
- b. 35 measuring cups
- c. 1 tube of Crest Cavity Protection Toothpaste, Regular (8.2oz) and
- d. 1 ClōSYS toothbrush

Each subject received the following supplies at Visit 2 i.e. supplies for 15-45 days:

- a. 2 bottles (16oz) of either Oral Rinse A or Oral Rinse X)
- b. 70 measuring cups
- c. 2 tube of Crest Cavity Protection Toothpaste, Regular (8.2oz) and

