The patients' data on the three measures were recorded within the Excel Workbooks under three tabs representing the first, second, and third clinical observation periods. So each tab recorded three measures. The first and last tabs recorded probing depth, gingival index, and plaque. The second visit included only gingival index and plaque. Each patient had an individual Excel Workbook. Data were sorted into analysis format through two Excel macros that created a single master data for global scores and a single one for implant and non-implant scores. Data files were saved in comma separated value (csv) format in both wide and long formats for R and SPSS data management, inspection, cleaning, and analyses.

Since many individual variable distributions varied substantially from normal, a gamma log-link function was applied to reduce bias in most statistical tests.

Label Key and Lot #s for Peri-Implant Mucositis Study with Stony Brook University

Rowpar Pharmaceuticals, Inc., released the test material label codes after completion of the clinical study and statistical analysis of the data. The products were labelled as follows:

Study Number: SBU-RPR-Peri-Implant Mucositis-2018

Oral Rinse A: ClōSYS Placebo Oral Rinse, Lot #: 2-80516

Oral Rinse X: ClōSYS® Ultra Sensitive (Unflavored) Oral Rinse, Lot #: 8122A 14-80430

Results

Patients

Fifty-two percent (29/56) of patients in both groups had only one implant. Patients in the control group (Group A) had a total of 47 implants: 11 patients had just one implant, 13 had 2, 2 had 3, and 1 had 4 implants. In the test group (Group X), there were 42 total implants in 26 patients: 18 had 1 implant, 9 had 2, and 2 had 3 implants (see Figure 1). Table 1 gives average values (and standard error of the mean) of Gingivitis Index, Plaque score, and Probing depth at baseline.

Figure 1. Bar chart of numbers of implants per person in control group (Group A) and test group (Group X).

[figure not shown]

Table 1. Patient dental measures at baseline.

		n of patients	n of implants	Modified Gingivitis Index (MGI) (sem)	Plaque score (PS) (sem)	Probing Depth mean (sem)
Control Group (Group A)	implants	27	47	2.06 (0.048)	2.77 (0.115)	3.40 (0.109)

	non-implanted teeth			1.87 (0.039)	2.32 (0.101)	2.72 (0.099)
Test Group (Group X)	implants	26	39	2.82 (0.049)	2.84 (0.057)	2.447 (0.080)
	non-implanted teeth			2.01 (0.028)	2.99 (0.078)	2.65 (0.079)

Global Score Analyses

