There is a clear advantage to using ClōSYS® Ultra Sensitive oral rinse treatment (test rinse X) in terms of plaque and gingival index. In addition, ClōSYS® Ultra Sensitive oral rinse (test rinse X) appeared to have a preferential benefit for implant sites, over both control treatment (placebo rinse A) and over non-implant sites. The ClōSYS® Ultra Sensitive rinse (test rinse X) significantly reduced the plaque index and gingival index as compared to initial measures and those in control group (placebo rinse A) ($p < 0.001$). The observation of higher initial gingivitis scores for the ClōSYS® Ultra Sensitive oral rinse (test rinse X) did not affect the superiority of this test group treatment. In controlling for the inequality at baseline, and analysis of covariance showed the reduction of the plaque score remained significantly better in the ClōSYS® Ultra Sensitive oral rinse group (test rinse X) than for the control group (placebo rinse A) ($p < 0.001$). Also, using pre-post difference scores and slopes of the scores over time showed the treatment effect to be robust to the mismatch of initial levels of gingivitis and plaque ($P < 0.001$ for both).

Both groups improved from the use of mouthwashes, but the ClōSYS® Ultra Sensitive oral rinse (test rinse X) improved more and at a faster rate ($p < 0.001$) compared to the control group (placebo rinse A). There was no apparent effect on periodontitis between the two intervals in which it was measured.

Implant sites were significantly more ($p < 0.001$) and faster ($p < 0.001$) improved in the ClōSYS® Ultra Sensitive oral rinse group (test rinse X) than the other non-implanted teeth and in the control group (placebo rinse A).

Both ClōSYS® Ultra Sensitive oral rinse (test rinse X) and placebo rinse (rinse A) tested are safe to oral tissues and did not show any adverse effects.

Both ClōSYS® Ultra Sensitive oral rinse (test rinse X) and placebo rinse (rinse A) tested are safe to oral tissues and do not have any adverse effects.

Signature Page

[name]

Principal Investigator

[name] [name], PhD

REFERENCES

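### The conclusion that neither rinse has any adverse effects has no reported safety data behind it; even zero events in 26 to 30 test patients would leave a two-sided 95% upper limit of 11.6% to 13.2%

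*Combined protocol and SAP*

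**What the plan says.** The Conclusions close with two near-identical sentences about both rinses. The first says that they "tested are safe to oral tissues and did not show any adverse effects". The second says that they "tested are safe to oral tissues and do not have any adverse effects". Neither gives a count or a denominator.

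Safety is in the title given in section [5] Protocol Synopsis, "The Efficacy and Safety of stabilized chlorine dioxide mouth rinse in Therapy of Peri-implant mucositis", although the objective stated there and in section [11] is efficacy only.

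The protocol does collect safety information:
- Section [9] has the oral mucosa evaluated for irritation or pathology at baseline, Day 14 and Day 90.
- Section [5] has Visit 2 "assess and record changes in indices and oral health and any adverse conditions".
- The first reason for withdrawal by the investigator is "An adverse event required discontinuation of the study rinse in the judgment of the Principal Investigator or designee". The same section provides for a close-out evaluation, an End of Study form and a record of causation.

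Section [11] then lists analyses of gingival index, bleeding on probing, plaque and probing depth. It defines no safety endpoint, safety population or adverse-event summary. The Results contain no safety data of any kind.

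**The concern.** The first sentence reports what was seen in this study. The second asserts a property of the products. Moving from one to the other needs a count, a denominator and a sample large enough to exclude the rates that matter, and the document supplies none of these. A reader cannot tell whether zero events were recorded, whether some were recorded and judged unrelated, or whether the record was never summarised.

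Because the title promises safety and the sentence names a marketed product, it is likely to be read and repeated as a trial finding. A study of this size and length could miss a fairly common local reaction. Section [9] also schedules no oral examination between Day 14 and Day 90, since Visit 3 covers compliance only. A mucosal reaction that came and went in that interval would be known only if the subject reported it.

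**Working it through.** The documents state no adverse-event rate, confidence limit or safety sample size, so there is no figure of theirs to reproduce. The check asks what the best case, zero events, would allow.

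**Test-arm size.** The sources conflict:
- Section [5] reports that "27 patients received 1) Stabilized chlorine dioxide".
- The Results say that "there were 42 total implants in 26 patients: 18 had 1 implant, 9 had 2, and 2 had 3 implants". That split adds to 18 + 9 + 2 = 29 patients, and to 18 + 18 + 6 = 42 implants.
- Table 1 prints 26 test patients and 39 implants.
- The Results also say "Fifty-two percent (29/56) of patients in both groups had only one implant". This agrees with 27 control patients (11 + 13 + 2 + 1) plus 29 test patients.
- Table 3 has N = 57, which leaves 57 − 27 = 30 test patients if control is 27.

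The totals are therefore 54 randomized (section [5]), 53 in Table 1 (27 + 26), 56 by the implant split and 57 in Table 3. The pooled plaque mean at time 1 in Table 3, set against the arm means in the text, gives 57 × (2.67895 − 2.35) / (3.00 − 2.35) = 28.8. So about 29 test patients fits the global analyses best. I carry the whole range of 26 to 30.

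**Upper limit with zero events.** One-sided 95%: 1 − 0.05^(1/n). Two-sided 95% (Clopper-Pearson): 1 − 0.025^(1/n).

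| Test patients | Source | One-sided | Two-sided |
|---|---|---|---|
| 26 | Results text, Table 1 | 10.9% | 13.2% |
| 27 | Section [5] | 10.5% | 12.8% |
| 29 | Implant split | 9.8% | 11.9% |
| 30 | Table 3 minus 27 control | 9.5% | 11.6% |

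The sentence covers the placebo rinse too. At 27 control patients its limits are those in the row for 27.

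**Chance of seeing at least one event,** 1 − (1 − p)^n:

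| True rate | n = 26 | n = 30 |
|---|---|---|
| 1% | 0.230 | 0.260 |
| 2% | 0.409 | 0.455 |
| 5% | 0.736 | 0.785 |
| 10% | 0.935 | 0.958 |

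An effect with a true rate of 2% would be missed altogether with probability 1 − 0.409 = 0.591 at n = 26.

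**Size needed.** To put the upper limit at or below 5% with zero events takes 59 exposed patients one-sided, ln(0.05)/ln(0.95) rounded up, or 72 two-sided. For 1% the numbers are 299 and 368.

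**The case against.** The strongest reply is that the second sentence looks like a drafting duplicate and the first is already limited to what was observed. That is fair, and deleting the second removes the worst of the overstatement. But the first still calls the rinses safe without qualification and still lacks a count and a denominator.

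A second reply is that safety was looked after: the mucosa was examined three times, and adverse-event withdrawals had a defined procedure. This stands. The absence of an adverse-event row in the section [4] schedule is largely a matter of labelling, and it would be wrong to infer that no safety data were collected. The gap is in analysis and reporting.

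A third reply is that the stated objective is efficacy only. That is true, and no efficacy result is affected. It makes an absolute safety conclusion harder to justify.

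A reader might also infer from the counts that three test patients and one control patient dropped out with their safety status unknown, so that the 26 are completers. There are hints of this. Going from 29 to 26 test patients matches the fall from 42 to 39 implants, 57 − 29 leaves 28 control patients against 27 in Table 1, and Table 3 has minimum scores of 0 at the last visit. The documents do not establish it, for four reasons:
- Table 1 is a baseline table, and nothing calls its patients completers.
- No control count of 28 is printed.
- Twenty-nine test patients exceed the 27 randomized, and totals of 56 and 57 exceed the 54 randomized, so withdrawal alone cannot explain the differences.
- Table 3 shows 57 patients at every time point.

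What is supported is that the counts conflict and disposition is not reported.

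Finally, pooling both arms would give a smaller limit. It would count placebo patients as exposed to chlorine dioxide, so it says nothing useful about the test product.

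**Conclusion.** The absolute safety conclusion is not supported and should not stand. No safety analysis is planned, no safety result is reported, and the most favourable reading, zero events, is compatible with a true adverse-event rate in the test arm of up to 11.6% to 13.2% (two-sided 95%) or 9.5% to 10.9% (one-sided 95%).

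This rests on two assumptions. Zero events is inferred from the first of the two sentences, because no count is printed; any recorded event would raise the limit. The test arm is taken as 26 to 30, and the conclusion is the same at every value in that range. The limits apply to about three months of use by patients meeting this trial's criteria.

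**What to change.** 1. In the Conclusions, delete the second of the two sentences, and remove the unqualified word *safe* from the first.
2. Reconcile the patient counts (54, 53, 56 and 57 in total; 26, 27, 29 or 30 in the test arm), and report by arm how many were randomized, received rinse, withdrew and were analysed, with reasons for withdrawal.
3. Add one table by arm, for everyone who received rinse, of adverse events, mucosal findings at Day 14 and Day 90, and withdrawals for an adverse event. Say that it is descriptive and was not specified in section [11].
4. Write the replacement sentence only after that table exists. State the observed number of test patients with an event, the reconciled denominator, and the exact 95% limit labelled as two-sided. If the count proves to be zero, the limit is the two-sided figure shown above for the reconciled denominator. If it is not, use the Clopper-Pearson interval for the observed count.

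The protocol already calls for these data, so the work is one table and some text. The price is a weaker safety claim.
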